## 12. The research involves the following procedures conducted by and for what purpose:

|  | PERFORMED BY:     |  | PROCEDURE IS:        |                                       |
|--|-------------------|--|----------------------|---------------------------------------|
| PROCEDURE  | Research
Staff | LSCDVAMC
Clinical or
Support Staff | Standard
of Care* | For
Research
Purposes
Only** |
| Audiotaping / Videotaping  | $\boxtimes$       |  |                      | $\boxtimes$                           |
| Attach VA Form 10-3203 REQUIRED ONLY FOR IN-PATIENT AND OUT-PATIENT SUBJECTS |                   |  |                      |                                       |
| Biopsy   |                   |  |                      |                                       |
| Blood collection   |                   | $\boxtimes$                              |                      |                                       |
| Chart review – prospective   | $\boxtimes$       |  |                      | $\boxtimes$                           |
| Chart review - retrospective   | $\boxtimes$       |  |                      | $\boxtimes$                           |
| Review of existing data (ex: registry, Database, etc.)                       | $\boxtimes$       |  |                      |                                       |
| X-ray or Ionizing radiation exposure   |                   | $\boxtimes$                              | $\boxtimes$          |                                       |
| Clinical Tests   | $\boxtimes$       |  |                      |                                       |
| Device implantation  | $\boxtimes$       |  |                      |                                       |
| Drug administration  |                   | $\boxtimes$                              | $\boxtimes$          |                                       |
| EEG, EKG, ECGetc   |                   | $\boxtimes$                              |                      |                                       |
| Gene therapy, Genetic analysis   |                   |  |                      |                                       |
| Pregnancy/Breastfeeding Screening  |                   | $\boxtimes$                              |                      |                                       |
| Interview, Questionnaire, Diary,
Survey (please attach)                   | $\boxtimes$       |  |                      | $\boxtimes$                           |
| Stool collection, Urine collection, or any Non-surgical Specimen collection  |                   |  |                      |                                       |
| Surgical procedure or Specimen removal during surgery                        | $\boxtimes$       |  |                      |                                       |
| Tissue banking (complete Section 12)   |                   |  |                      |                                       |
| Use of pre-existing tissues/specimens  |                   |  |                      |                                       |
| Other (list): dual-energy x-ray absorptiometry (DEXA)                        |                   |  |                      |                                       |

 \*Standard of care procedures are procedures performed in the course of normal medical care.

 \*\*Research Procedures are performed for the purposes of this research alone.

## 13. Please describe the research design and all study related procedures.

- Describe ALL PROCEDURES ASSOCIATED WITH THIS RESEARCH. This includes standard of care and research procedures.
- For complex studies please include diagrams and tables. Be sure to describe when each procedure will be performed. Be sure to provide information for each cohort, including normal controls).

Study design:

For all new subjects receiving an implanted neuroprosthetic system, a screening process will occur as inpatient or outpatient, dependent upon the subject's geographic location and level of injury. After the screening, and prior to implantation, an exercise training program will be initiated. Implant surgery may include up to 9 days hospitalization prior to returning home. After the subject has healed from the surgical implant an exercise plan will resume on an outpatient basis to achieve goals using the implanted system. During the final testing and experimentation phase the system will be customized and fine tuned. This final phase may include up to an additional 50 days for customization and system tuning, dynamometer tests of strength and fatigue, standing duration, and body weight distribution and stability.

Screening (Phase I): Participation begins with a screening evaluation and informed consent. After informed consent a series of physical examinations will be performed by a qualified clinical staff to assess medical status and candidacy for the implanted neuroprosthesis. These evaluations include motor and sensory evaluation, nerve and muscle excitability with surface stimulation or intramuscular probe, joint status, bone density, baseline standing capability without FNS or with surface stimulation, and cardiopulmonary status. If psychosocial issues are suspected with a potential participant, he/she will be asked to see their primary care physician who may refer them to a psychologist for screening. The psychologist will use the instruments that, in their best judgment, will yield a diagnosis or resolve uncertainty surrounding a potential participant's suitability for the project. If the psychosocial screening indicates that the potential participant is not well suited to this project in terms of their ability to tolerate uncertainty and cope with the demands of the research project, their participation will be terminated. If the above steps yield satisfactory outcomes, participants will undergo a period of preparatory exercise with surface stimulation followed by muscle strength re-evaluation prior to implant surgery.

Prior to implantation, a medical history review and physical examination are performed, including an ASIA Impairment Scale examination to assess the subject's level of motor and sensory impairment as defined in the International Standards for Neurological and Functioning Classification of Spinal Cord Injury. Blood analysis, urine analysis, EKG and chest X-rays (according to anesthesia standards) may be required to identify any conditions that would rule out the surgery. AP and lateral images of the hips, knees and ankles will be obtained to document baseline joint status and identify any abnormalities that may contraindicate surgery and weight bearing. Measures of bone mineral density via DEXA scan may also be obtained to assess the potential for weight bearing. Copies of the informed consent are provided to each participant for their review.

During the screening evaluation process, it may be discovered that a subject is eligible for multiple studies or that they may be a better candidate for a different protocol. The subject may be referred to other studies they are eligible for.

Screening subjects with previously implanted neuroprosthesis will undergo screening procedures as necessary to determine their eligibility in this study. In addition, existing data will be used for evaluation of eligibility. Repeat testing to determine eligibility in this study may be necessary depending on individual circumstances and the amount of time elapsed since the last exam or test was completed.

Surgical Procedures and Implantation (Phase II):

After identifying key muscles for stimulation, one or more implanted stimulator telemeters (ISTs) will be implanted. Prior to surgery, motor points of the muscles targeted for activation will be mapped with surface stimulation and marked. If selected individuals are not clinically well suited to receive multi-contact nerve cuffs on their femoral nerves, intramuscular electrodes will be inserted at the motor points of each individual head of the quadriceps (vastus lateralis, medialis and intermedius, and rectus femoris) to selectively activate separate and independent motor unit pools.

Nerve cuff electrodes (CWRU spiral, Flat Interface Nerve Electrode (FINE), or Composite-Flat Interface Nerve Electrode (C-FINE) will be deployed in an open surgical exposure of the proximal femoral nerve. Fluoroscopic examination of the lumbar spine (between T11 and L2) will be used during electrode implantation for the erector spinae (trunk extension) or other muscles. The function of all electrodes will be verified intraoperatively before final subcuticular closure and dressing. Anterior-Posterior X-rays of the region from the xiphoid to the mid-shanks will be obtained to document the status of the implanted electrodes, connectors and control device.

Post-operative management, exercise and training includes hospitalization for up to nine days days for monitoring, incision management and therapy to maintain range of motion and increase sitting tolerance, followed by discharge to home with specific instructions to avoid activities that might put stress on the incisions and implanted components, observe the incisions for signs of infection, and note any significant increase or decrease as well as changes in the pattern of spasticity (flexion/extension). Any medical problem suspected after surgery may require an extension to the hospital stay.

At approximately 6 weeks post-surgery, or earlier if incisions are sufficiently healed, stimulated responses will be characterized and exercise with the implanted neuroprosthesis will be initiated. Recruitment properties (stimulus thresholds, manual muscle grades, spillover or reflex activation) of each electrode or contact within a nerve cuff will be recorded. The stimulated responses of the implanted electrodes will be incorporated into initial exercise patterns that will be constructed for each individual. Participants then begin a reconditioning program of progressive resistance strengthening and endurance exercises with stimulation customized to their rate of progress. The exercise program consists of established protocols for both strength training (few repetitions at maximal load via ankle weights) and endurance (high number of repetitions at low loads). These exercises may include contracting the muscles against loads using weights or resistive bands and commercially available exercise equipment. Subjects are expected to complete this exercise program prior to initiating standing, dynamometer and other tests of continuous stimulation or the fatigue delaying stimulation paradigms in order to ensure that their muscles are maximally conditioned and as fatigue resistant as possible.

Standing, pivot transfers and balance training follow the exercise phase until implant recipients demonstrate mastery of basic standing functions with the system, which can take several months. The users will undergo extensive training to learn basic sit-to-stand and quiet standing functions with continuous stimulation. A qualified clinical study staff may measure the strength and range of motion of the voluntary musculature and perform a full ASIA Sensory and Motor Evaluation during

follow-up approximately 1 year after discharge from post-implant rehabilitation. A follow-up DEXA may also be completed approximately 1 year post-rehabilitation to measure change in bone density.

Subjective ratings of physical and medical health, emotional health, social participation, and physical functioning will be obtained by administering a multiple-choice questionnaire, the Spinal Cord Injury-Quality of Life (SCI-QOL), at baseline and at follow-up intervals after rehabilitation and training is completed for comparison against baseline ratings.

Video recordings may be done during all experiments to help with data analysis and for display

during talks, seminars and workshops.

All surgical and evaluation procedures will take place at the LSCDVAMC. [name] will be responsible for surgical implantation of the systems and preoperative clinical management, and [name] will be responsible for medical clearance for recruitment and enrollment and daily management of clinical issues associated with the project. Alternatively, and only if necessary depending on availability of the operating room at LSCDVAMC, implantation can take place at MetroHealth Medical Center at which [name] has and maintains operative privileges.

#### Testing and Experimentation (Phase III):

Once training is completed, the subject will commence with the testing phase to assess the performance of the implanted system.

Implementation of the fatigue delaying paradigms is essentially a three-step process.

- 1.) Stimulation parameters must be chosen to produce strong muscle contractions with little or no overlap in the populations of motor units activated. This step will be accomplished with the subject positioned in a dynamometer while stimulation parameters are varied by a computer-controlled optimization algorithm to create non-overlapping recruitment curves. [6].
- 2.) Using the values that specify non-overlapping stimulation as an upper limit, patterns must be tuned to produce the desired profile of joint torque, such as ramping up, plateau time, and ramping down for carousel stimulation, or sinusoidal oscillation frequency and pulse width values for the SOPS paradigm. For the carousel and SOPS paradigms, it is important to ensure that the maximum joint torques generated by stimulating through individual contacts are balanced and roughly equivalent to each other to avoid ripple (jitter or oscillations) in the output when they are combined.
- 3.) Joint torque will be recorded on the dynamometer during each stimulation pattern and ripple will be quantified to ensure that a constant contraction is achieved.

These three steps can be completed in approximately five two-hour long sessions.

Biomechanical Tests Strength and Endurance: Once stimulation patterns have been hand-tuned to produce strong, low-ripple contractions for each of the fatigue delaying stimulation regimes, tests of their functional impact on fatigue will be performed. To quantify the rate of fatigue of each paradigm isometric fatigue tests will be performed on the dynamometer with the knee held in 20° of flexion. Each fatigue test will consist of approximately 30 minutes of stimulation with a particular paradigm. Fatigue tests for all four conditions (SOPS, carousel, interleaved and baseline continuous stimulation) will be repeated for both legs nominally three times in random order for each subject, with never more than one fatigue test per leg per day.

Standing Time and Body Weight Distribution:

Each stimulation regime will be included in a standing pattern that allows the subject to use maximal continuous stimulation to execute the sit-to-stand transition and then switch the knee stimulation pattern to one of the fatigue delaying paradigms. Hip and trunk stimulation will remain

consistent throughout all trials at the levels that were determined to be most effective clinically for each individual to isolate the effects of the fatigue delaying regimes on knee extension. The subject will be instructed to stand for as long as possible with feet on a set of force plates and hands on a set of load cells to measure the distribution of body weight through the arms and legs. Standing posture can be monitored during these tests with a digital motion capture system to ensure consistent orientation of the body in order to control for variations in hand and foot placement or alignment of the head, trunk and pelvis. No more than one standing test will be performed per day, and the duration of each stand will be recorded. A stand will end either when a subject decides to sit, a physical therapist notes knee buckling, or more than 20% of body weight is supported by the arms for more than 3 seconds. Stands lasting more than 10 minutes will be considered functionally relevant, as this would represent more than a doubling in maximum standing time for more than half of the subjects using continuous stimulation in our prior studies [4].

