## 10. Describe the means of analyzing the data and evaluating the results.

- State the anticipated methods to be used for analysis and interpretation of the data.
- The methods must compliment the design of the study and the nature of the data which is being collected.

This study takes the form of a case series and employs the principles of single-subject research design. Each subject acts as his or her own concurrent (differences among stimulation paradigms for the individual at the same time interval) and longitudinal (initial post-exercise and training measurement versus follow-up values) controls. Primary statistical analyses will be in

comparison to the continuous stimulation case and will be performed on each subject individually. The effect sizes for these analyses were estimated using data obtained from existing 8-channel users and assuming a power level of 80%.

- 1. The longitudinal stability of the optimal stimulation parameters (pulse width and amplitudes) to ensure selective and non-overlapping activation of different muscles with each contact within the nerve cuffs will be assessed via a two-tailed t-test between initial and follow-up measurements.
- 2. Differences among the fatigue-delaying stimulation paradigms (carousel, interleaved, sum of phase-shifted sinusoid) and in comparison to continuous stimulation in terms of biomechanical measures of fatigue (T50, T0.21) and isometric strength will be determined by ANOVA performed on repeated measures of the outcome variables at each measurement interval.
- 3. Standing performance in terms of elapsed standing time and body weight distribution on the arms and legs will be compared across stimulation paradigms for each subject via ANOVA.
- 4. Standing stability in terms of variations in knee joint angle and location of body center of mass while standing with various stimulation paradigms will be assessed via ANOVA. The Wilcoxon Ranked Sum Test will be applied to the seven point ordinal data related to the subjective impressions of stability.

Tests will nominally be repeated three times in random order and the resulting body weight distribution and elapsed standing durations will be compared via ANOVA to determine the relative performance of each stimulation paradigm.

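### Test order is random but not stated to be balanced over time or modelled; complete blocks with a session term are a cheap improvement, and the two daily test limits need reconciling

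*Combined protocol and SAP*

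**What the plan says.** Item 13, Testing and Experimentation (Phase III), names the conditions compared on the dynamometer: "Fatigue tests for all four conditions (SOPS, carousel, interleaved and baseline continuous stimulation". On repetition and order, it says of these tests that they "will be repeated for both legs nominally three times in random order for each subject". Item 10 ends with a general statement that also covers the standing tests: "Tests will nominally be repeated three times in random order". Neither item says how the order is generated, or whether each paradigm must appear once before any is repeated. The randomization box in item 14 is ticked No. That probably refers to allocating subjects to groups, but no ordering procedure appears elsewhere either.

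On analysis, item 10 says the primary comparisons are with continuous stimulation and "will be performed on each subject individually". Differences in the fatigue measures "will be determined by ANOVA performed on repeated measures of the outcome variables at each measurement interval". No term for session, day or block is named there or for the standing outcomes.

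Two daily limits apply. Fatigue tests are run "with never more than one fatigue test per leg per day". For standing, "No more than one standing test will be performed per day". On the length of a fatigue test: "Each fatigue test will consist of approximately 30 minutes of stimulation with a particular paradigm".

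**The concern.** Each subject gives 12 stands (four paradigms, three times each) and 12 fatigue tests per leg. The daily limits spread each series over at least 12 days. In a plain random order, one paradigm can by chance fall mostly early and another mostly late. If performance drifts over those sessions, the drift enters the difference between the two paradigms. Because the primary analysis is done subject by subject, the imbalance is not averaged out over 15 subjects.

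Some drift is plausible for standing. The standing training described in item 13 uses continuous stimulation, so the new paradigms are less practised when the stands begin.

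The daily limits raise a separate point. Each caps its own test type and neither mentions the other. A stand to fatigue on the same day as about 30 minutes of stimulation to the same knee extensors is therefore permitted, although elapsed standing time is a main outcome and quadriceps fatigue is what is meant to end it.

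**Working it through.** **Inputs from the documents.** 4 paradigms × 3 repeats = 12 tests per series, with one series of stands and one fatigue series per leg. Analysis is per subject, with no order term. The plan gives no figure of its own for order balance, drift or test-to-test SD, so there is nothing to reproduce.

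**Assumptions.** Independent normal errors with SD 1; a linear drift of D residual SDs from test 1 to test 12, common to all paradigms; two-sided alpha 0.05; no carry-over term.

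**Step 1: balance of position.** The variance of positions 1 to 12 (divisor 11) is 13; that of positions 1 to 4 within a block (divisor 3) is 5/3. The SD of the difference in mean position between two paradigms is:

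- unrestricted: √(2 × 13/3) = 2.94 slots
- three complete blocks: √(2 × (5/3)/3) = 1.05 slots

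In simulated orders, at least one new paradigm averages 4 or more slots from continuous in about 45% of unrestricted orders and 0% of blocked ones. Continuous has all three repeats in one half of the series in 2 × C(6,3)/C(12,3) = 40/220 = 18% of unrestricted orders. For fatigue tests, averaging two independently ordered legs gives 2.94/√2 = 2.08 slots, and the 45% falls to about 15%.

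**Step 2: noise added to a contrast.** The slope is D/11 per slot. The variance of a paradigm difference is multiplied by 1 + (D/11)² × 13 if unrestricted, and by 1 + (D/11)² × 5/3 if blocked:

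- D = 1: 1.11 against 1.01
- D = 2: 1.43 against 1.06
- D = 3: 1.97 against 1.12

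Unrestricted, the SD of a contrast therefore rises by 5%, 20% and 40%.

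**Step 3: power in one 12-test series, true difference 2 SD** (simulation; the error df allow for the added term).

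| Order and model | Error df | D = 0 | D = 1 | D = 2 | D = 3 |
|---|---|---|---|---|---|
| Unrestricted, no term | 8 | 58% | 54% | 43% | 33% |
| Blocks, block factor | 6 | 54% | 53% | 51% | 49% |
| Blocks, linear session term | 7 | 55–56% | 55–56% | 55–56% | 55–56% |
| Blocks, no term | 8 | 58% | 52% | 39% | 23% |

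Type I error for the unrestricted design, averaged over orders, stays at 5.0% to 5.4%. The last row shows that blocking without modelling it does not help: the drift moves into the error term.

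**Step 4: two-leg fatigue tests (24 tests).** For a true difference of 2/√2 = 1.41 SD, power with no drift is about 64% both for unrestricted order and for blocks with a block factor. At D = 2 it is about 49% and 60%.

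**Step 5: the daily limits side by side.** The fatigue limit is per leg per day and the standing limit is per day. Neither refers to the other type, so a stand on a fatigue-test day is permitted. The calendar does not force it. Taking each session as one day, about five tuning sessions + 12 fatigue days + 12 standing days = 29, or 5 + 24 + 12 = 41 with legs on separate days. Item 13 allows up to 50. The documents give no recovery time, so the size of any carry-over cannot be computed.

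**The case against.** The strongest reply is that the drift is assumed. Item 13 expects the exercise programme to be finished before testing, so that muscles are already conditioned, and standing training continues until basic function is mastered. If drift is small, the present design loses little and a block factor costs power. Per subject, error df fall from 8 to 6, the critical t rises from 2.31 to 2.45, and power drops from 58% to 54% at zero drift. The block factor gains only above about 1 SD of drift. This stands. The cost cannot be dismissed by appeal to pooling, because the primary analysis does not pool. The counterweight is that a linear session term costs only about 2 points in a 12-test series, and two-leg fatigue tests lose essentially nothing.

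Second, the wording also fits three rounds, each in random order, and a repeated-measures ANOVA could contain terms that the plan does not list. This stands too: the unrestricted order is read from silence. If rounds are intended, one sentence settles the ordering, but the model term is still needed.

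Third, a reader might infer that paradigm is confounded with time, so that results would be biased. The documents do not support that. A lopsided order does displace that subject's estimate: a gap of 4 slots at 2 SD of drift shifts it by 4 × 2/11 = 0.73 SD. But random ordering makes the displacement equally likely in either direction, and type I error over orders stays near 5%.

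**Conclusion.** The point holds as a cheap improvement. The order is not stated to be balanced and no order term is named, so chance imbalance in time can add noise to each subject's comparisons. If the order is unrestricted, the position gap between two paradigms has an SD about 2.8 times as large as with blocks (2.94/1.05). What that costs depends on a drift the documents do not give: little at 1 residual SD or less over the 12 tests, and about 15 points of power at 2 SD for a 2 SD difference (58% to 43%). There is little precision to spare, since three repeats per paradigm with 8 error df already need a difference of 2.6 SD for 80% power. These figures assume linear drift common to all paradigms. Practice that helps only the new paradigms would not be removed by a common session term, although blocks would still balance its timing.

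A reader might also infer that stands will be run on fatigued muscles. The documents permit same-day testing by omission. They do not plan it, and nothing in them shows carry-over or its size.

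**What to change.** - **Order.** State in items 10 and 13 that it is generated in three complete blocks: each paradigm once per block, in a fresh random order, with separate lists for fatigue tests (per leg) and standing tests.
- **Model.** Name session order in the per-subject analysis, as a linear term (1 df) or a block factor (2 df), chosen before data are seen. Blocks and term belong together.
- **Spacing.** The investigators should reconcile the fatigue-test and standing-test limits in item 13 and state how the two test types are separated. Any interval is theirs to set.

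The cost is a different order list and a few sentences. With no drift, the stands lose about 2 points of power with the linear term or about 4 with the block factor, and two-leg fatigue tests lose essentially none. At 2 SD of drift, the stands gain about 12 points with the linear term (43% to 55%) or about 8 with the block factor (43% to 51%).

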#### THE HYPOTHESES TO BE TESTED ARE:

- The knee joint torques generated by fatigue delaying stimulation paradigms will be sufficient to keep the knees locked during standing for at least 10 minutes. This will be tested by tracking how long the knee can produce an extension torque on the dynamometer that exceeds a threshold set for each subject based on their body weight. [5.]
- Standing with fatigue delaying stimulation paradigms will be more stable and of longer duration
  than constant stimulation. This will be tested by recording the elapsed standing times before
  system users are required to sit due to fatigue of the quadriceps muscles for each of the
  advanced stimulation waveforms, as well as by monitoring variations in knee angle and
  subjective impressions of stability while standing.
- Clinical performance of the fatigue delaying stimulation paradigms will be stable over time. This
  will be tested by repeating the tuning procedures and comparing the optimal parameters over
  time, repeating dynamometer testing of the same stimulus paradigm at various time intervals,
  and repeating stand-to-fatigue, body weight distribution and stability tests in the laboratory.
- Objective optimization of control parameters will lead to longer sustained contractions before
  fatigue. This will be tested by comparing the knee extension torque produced by hand tuning the
  stimulation paradigms to the outcome applying the automated and objective optimization
  process for setting up stimulus parameters. These experiments can be performed primarily on
  the dynamometer and verified during standing in the laboratory.

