#### Stability and User Perceptions of Stability:

Kinematic data collected by the motion capture system during the stand-to-fatigue and body weight distribution trials described above will be used to quantify the stability of the stimulation strategies.

Subjective perceptions of stability will be assessed with the Usability Rating Scale (URS). The URS will be adapted to assess subjective perception of stability and applied immediately after every standing test with each stimulation paradigm. Subjects rate only their impression of the task just completed and are not asked to make mental comparisons to past performance under the same or other conditions. Positive significant differences from zero of the change scores will indicate improved perception of stability while negative significant differences will indicate reduced perception of stability.

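### Standing time can end on the subject's own decision and perceived stability is self-rated, yet nothing in the plan masks the stimulation paradigm, so expectation can bias both

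*Combined protocol and SAP*

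**What the plan says.** **How a stand ends.** Item 13 (Standing Time and Body Weight Distribution) gives three triggers: "A stand will end either when a subject decides to sit, a physical therapist notes knee buckling", or the arms carry over 20% of body weight for longer than 3 seconds. The third is read from load cells under the hands. The effort instruction is: "The subject will be instructed to stand for as long as possible with feet on a set of force plates".

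**How the hypothesis describes the same outcome.** The second hypothesis in Item 9 speaks of the time elapsed before "system users are required to sit due to fatigue of the quadriceps muscles for each of the" advanced waveforms.

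**How stability is assessed.** There is a self-rating: "The URS will be adapted to assess subjective perception of stability and applied immediately after every standing test with each stimulation paradigm". It carries a safeguard: "Subjects rate only their impression of the task just completed and are not asked to make mental comparisons to past performance". There is also an instrumented measure, analysed by ANOVA under Item 10: "Standing stability in terms of variations in knee joint angle and location of body center of mass while standing with various stimulation paradigms".

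**What subjects know of the comparator.** Before testing, per Item 13, "The users will undergo extensive training to learn basic sit-to-stand and quiet standing functions with continuous stimulation".

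**Masking.** Neither the design nor the analysis items describe withholding the paradigm from the subject or the therapist. The only mention of blinding is standard form text in Section 10 on devices. Item 10 does put the tests in random order, nominally with three repeats.

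**The concern.** The second hypothesis rests on three kinds of evidence: standing duration, variation in knee angle, and the subject's impression of stability. The first and third depend partly on the judgement of someone who may know which pattern is running. A subject hoping for the new paradigm to work may hold on a little longer with it, give up a little sooner with the familiar continuous pattern, or rate the new one as steadier. A therapist calling buckling may be influenced in the same way.

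Random order balances sequence and fatigue effects, but it does not stop anyone knowing which paradigm is active. If expectation ran the same way in most subjects, a shared bias could be taken for the generalizability that Item 8 sets out to show.

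**Working it through.** **1. Which outcomes are exposed.**

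| Outcome | What determines it | Open to expectation? |
|---|---|---|
| Stand ended by the subject sitting | Subject's decision | Yes |
| Stand ended by buckling | Therapist's observation | In part |
| Stand ended by arm load | Load cells, 20% of body weight for over 3 seconds | Largely no |
| URS | Subject's rating | Yes |
| Knee angle, centre of mass | Motion capture | Largely no |
| Isometric fatigue and strength | Dynamometer | Largely no |

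**2. The two definitions side by side.** The hypothesis in Item 9 counts time until quadriceps fatigue forces the user to sit. The rule in Item 13 also counts a sit by choice, for any reason. Item 13 asks for the duration of each stand to be recorded but not the reason it ended, so the two kinds of ending could not be separated afterwards.

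**3. Limits on the mechanism.** The knee is held by stimulated muscle, so willingness cannot keep it extended once the muscle fails. Shifting weight to the arms ends the stand at the load limit. Expectation can therefore lengthen a stand only up to buckling or the arm-load limit. Nothing comparable limits how early a subject may sit under continuous stimulation.

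**4. Scale for the planned per-subject analysis (assumed inputs).** The primary analyses are done on each subject separately. Take 4 paradigms with 3 stands each, one-way ANOVA, two-sided alpha 0.05 (assumed; the plan states none), no true effect, and an expectation shift of *b* between-stand SDs in all three new paradigms.

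- Group means are (0, *b*, *b*, *b*), with overall mean 0.75*b*.
- Sum of squared deviations is (0.75*b*)² + 3 × (0.25*b*)² = 0.75*b*².
- Noncentrality is 3 × 0.75*b*² = 2.25*b*², with 3 and 8 degrees of freedom.

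| Shift *b* (SD) | Noncentrality | Chance of a false difference |
|---|---|---|
| 0 | 0 | 5% |
| 0.25 | 0.14 | 5.5% |
| 0.5 | 0.56 | 7% |
| 1 | 2.25 | 15% |
| 2 | 9 | 49% |

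**5. Scale in minutes (assumed inputs).** If 30% to 60% of stands end by choice and expectation prolongs those by 10% to 30%, mean standing time rises by 0.30 × 0.10 = 3% to 0.60 × 0.30 = 18%. This applies no cap from buckling or arm load. A prolonged stand would cross the 10-minute relevance mark only if it would otherwise have lasted about 10/1.30 = 7.7 to 10/1.10 = 9.1 minutes or longer.

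None of the inputs in steps 4 and 5 comes from the documents. They show what a bias of a given size would do, not what the bias is.

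**The case against.** The strongest reply is that the plan already guards much of this ground.

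- Arm load is an instrumented trigger, and it closes the obvious route to a longer stand.
- The URS asks only about the stand just completed.
- Item 38 has staff stress repeatedly that improvement is not guaranteed.
- The kinematic and dynamometer measures involve no decision to sit.
- Long training on continuous stimulation might favour the familiar pattern instead of the new ones.
- Even an 18% rise turns a 5-minute stand into 5 × 1.18 = 5.9 minutes, far from the 10-minute mark.
- Masking may fail. Subjects meet the patterns in tuning and fatigue tests, some have sensation, and the switch of knee pattern after rising may itself reveal the condition.

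Most of this stands, and it limits the point to voluntary sits, calls of buckling and the URS. It does not remove it. The arm-load limit does not affect a free decision to sit, asking for no comparison does not hide the condition, and imperfect masking is still better than none.

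Several stronger readings are tempting but unsupported:

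- **Stability rests on self-report.** It does not; knee angle and centre of mass are analysed too.
- **The self-rating lengthens stands.** It is taken after the stand and cannot.
- **Subjects are told the pattern.** The plan is silent on this, and the consent text is not among the documents.
- **The bias must favour the new paradigms, by 3% to 18%.** The direction is not established, and that range is built entirely from assumptions.

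**Conclusion.** The point holds in limited form. With no masking planned, expectation can bias stands that end by choice, calls of buckling to a lesser degree, and every URS score. Kinematic stability and dynamometer fatigue are largely protected. That the testing is unmasked is inferred from the absence of any masking provision.

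The size and direction of the bias cannot be derived from the documents. Under the assumptions shown, the planned per-subject ANOVA is only mildly affected by shifts up to about 1 SD (a false-difference rate of 15%, against 5% nominal) and seriously affected near 2 SD (49%). A reader might infer far worse from pooling subjects: a paired test with 15 subjects would give 44% and 95% at shifts of 0.5 and 1 SD of the within-subject differences. That is not the plan's primary analysis.

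Separately, Items 9 and 13 describe the end of standing time differently and must be reconciled. This is a cheap improvement that should be made, not a fatal flaw.

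**What to change.** 1. In the standing tests, load the four knee patterns under neutral codes, re-coded for each subject, and do not tell the subject which is active. Give the continuous condition an equivalent dummy switch after sit-to-stand, so that the switch does not identify it.
2. Mask the therapist who calls buckling only where existing staffing allows and the contact guarding described in Item 40 is unaffected.
3. After the URS, ask the subject to guess the pattern, and report how often the guess is right.
4. Record which of the three triggers ended each stand.
5. Pre-specify a sensitivity analysis of standing time that treats voluntary sits separately, for example as censored or as competing events. Censoring assumes that the decision to sit is unrelated to approaching fatigue, which is doubtful, so report the trigger counts by paradigm beside it. With about three stands per paradigm per subject, this will be largely descriptive within a subject.
6. Reconcile the wording of standing time in Item 9 with the stopping rule in Item 13.

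**Cost.** Pattern labelling, one dummy step, one question and one recorded field. Masking the subject needs no new staff; masking the therapist depends on who runs the stimulator, which the plan does not say. The downside is that masking may be incomplete because of earlier exposure to the patterns and preserved sensation. The guess question and the recorded end reason let that be reported.
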